Based on pre-clinical data, copanlisib began testing in a phase 1 dose escalation first in human study, 12871 in patients with advanced cancers. A dose of 0.8mg/kg was determined to be the maximum tolerated dose in non-diabetic patients. Dose limiting toxicity was acute hypertension at 0.4mg/kg in one patient and left ventricular systolic dysfunction with ischemic EKG changes and lactic acidosis at 1.2 mg/kg in another patient consistent with safety studies in dogs. Increased BP was frequently observed within the first 3 hours of infusion which needed antihypertensive therapy. Adverse events noted in more than 20% of patients include hyperglycemia (63.2%), nausea (38.6%) and hypertension (21.1%). Most common grade 3 AE but regardless of seriousness and causality, occurring in >5% of the 57 patients were: hyperglycemia (33.3%), hypertension (19.3%), anemia (7.0%) and AST increased (5.3%). Three Follicular Lymphoma patients experienced any treatment-emergent interstitial pneumonitis, all with a severity of Grade 3 and assessed as serious. Of note, no pneumonitis was reported in the 48 patients with solid tumors treated in this study. Study 16790 is a phase 1 PD study to evaluate effects of PD biomarkers in patients with NHL and selected solid tumors at 2 dose levels, 0.4mg/kg and 0.8 mg/kg. Diabetic patients are allowed to be treated on 2 cohorts in this study at a flat dose of 45 mg and 60mg and only one patient has been treated so far. Most common TEAEs of any grade occurring in more than 20% of patients on study 16790 were hyperglycemia and fatigue (37.5%), hypertension (33%), anemia and nausea (25%), as well as diarrhea (20.8%). This study is ongoing and PTEN or PI3K mutation status is unknown at this time. Three phase 1 studies, (12874, 12875 and 1276) are ongoing which were done to determine MTD of copanlisib in combination with paclitaxel, gemcitabine+ cisplatin and refametinib (MEK inhibitor). Study 16270 is evaluating potential drug interactions of copanlisib with itraconazole (a strong CYP3A4 inhibitor) and rifampin (a strong CYP3A4 inducer). A healthy volunteer study, 16353 was completed with a dose of 12 mg of copanlisib and was well tolerated. Study 15205 is a single agent dose escalation study in 10 Japanese patients with advanced solid tumors. In this study, PK samples were collected from 3 Japanese patients at the 0.4 mg/kg dose level and seven patients at the 0.8 mg/kg dose level. Exposures of copanlisib increased in a roughly dose proportional manner. The plasma concentration-time profiles were similar between Japanese and non-Japanese patients at both the 0.4 mg/kg and 0.8 mg/kg dose level. Treatment emergent AE of all grade in more than 20% of patients in study 16349 which is limited to non-Hodgkin's lymphoma included hyperglycemia (56.8%), hypertension (53.1%), diarrhea (33.3%), neutropenia (23.5%), and fatigue (21.0%). Hyperglycemia peaked 5 to 8 hours after treatment and was reversible. This is an expected on target effect as PI3K is required for downstream signaling from the insulin receptor. Inhibition of this pathway leads to impaired uptake of glucose with a reactive rise in plasma insulin and glucose levels.

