3.5 Dose Modifications

All toxicity grades below are described using the NCI Common Terminology Criteria for Adverse Events (CTCAE) version 5.0.

All appropriate treatment areas should have access to a copy of the CTCAE version 5.0. A copy of the CTCAE version 5.0 can be downloaded from the CTEP website

(http://ctep.cancer.gov/protocolDevelopment/electronic_applications/ctc.htm).

The side effects observed with copanlisib (BAY 80-6946) are consistent with those observed with other PI3K inhibitors.

Copanlisib will be administered at fixed dose (60 mg) intravenously on Days 1, 8, and 15 on a 28-Day cycle. Copanlisib dose reduction instructions provided in **Table 1** serve as guidelines to allow ongoing treatment for patients without signs or symptoms of progression while monitoring patient safety. If there is need to interrupt dosing for grade 3/4 toxicity, then there will be a dose reduction as per the table below, once toxicity improves to grade 1 or baseline. Selected toxicities / adverse events of interest for copanlisib include hyperglycemia, rash, hypertension, diarrhea.

Table 1 Overall Dose Modification Guideline for Copanlisib (BAY 80-6946)-Related Adverse Events

	Copanlisib
Starting dose	60 mg
First reduction	45 mg
Second reduction	30 mg

Dose may be suspended for up to 4 weeks due to toxicity. Patients requiring treatment to be held for >4 weeks will be taken off treatment. If treatment held for laboratory abnormality, recheck labs in one week. No dose reduction is allowed for patients treated at a dose 30 mg of copanlisib – if there is an indication for further dose reduction, the patient must permanently discontinue copanlisib. Dose re-escalation is not allowed after a dose reduction.

Rev. Add16

Dose Modification rules for transient post-infusion hyperglycemia

Patients who develop post-infusion glucose increases of grade 2 after study drug administration may continue treatment. However, the next infusion must be delayed until the patient's pre-infusion glucose levels return to < 160 mg/dL (fasting) or < 200 mg/dL (non-fasting). Guidelines for the management of transient glucose increases are given in [Appendix III](#). Continuing occurrence of post-infusion blood glucose increases of grade ≥ 3 despite optimal glucose lowering therapy after 2 infusions of copanlisib, will require dose reduction by one dose level.

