(Scenario D)	
 • Refractory hypertension unresponsive to above interventions or hypertensive crisis. 	
 • Continue follow-up per protocol. 	
 • Discontinue copanlisib.

Non-infectious pneumonitis

The investigator is requested to differentiate between non-infectious pneumonitis, and infectious pneumonitis (viral, bacterial, or fungal), aspiration pneumonitis, or other pneumonitis clearly not due to a potential hypersensitivity reaction to the copanlisib infusion; and provide the basis for his/her assessment that it is infectious or other, as appropriate. The investigator is requested to report with the most specific clinical terms to describe the condition, not simple “pneumonitis”.

In the event of suspected non-infectious pneumonitis, modify copanlisib treatment as per table below.

Dose adjustment for non-infectious pneumonitis

Suspected or confirmed NIP per CTCAE	Action Taken	Re-treatment dose after recovery
Grade 1	No Change	NA
Grade 2	Dose Interruption Until recovery to \leq grade 1	Decrease dose to the next lowest dose level ^a
Grade 2 second re-occurrence	Permanent Discontinuation	NA
Grade 3	Permanent Discontinuation	NA
Grade 4	Permanent Discontinuation	NA

NA = Not applicable; NIP = Non-infectious pneumonitis; CTCAE = Common Terminology Criteria for Adverse Events.

a: Not applicable for 45 mg dose level. No re-escalation is allowed after the dose reduction.

Rev. Add16

The lowest dose level for patients with non-infectious pneumonitis is 45 mg; if a patient is already on the 45 mg dose level and cannot tolerate treatment study treatment will be discontinued permanently.

Rev. Add16

Dose modifications for Hematological Toxicities

Day	ANC		Platelets	Dose modifications
Day 1	$\geq 500/\mu\text{L}$	AND	$\geq 75,000/\mu\text{L}$	Treat at current dose level
	$< 500/\mu\text{L}$	OR	$< 75,000/\mu\text{L}$	Delay until count recovery

Use of WBC growth factors is allowed as per institutional guidelines for treatment or prevention of complication. Use of WBC growth factors to maintain dose intensity is not allowed.

Dose Modifications for General Non-hematologic Toxicities

This section does not refer to those non-hematologic toxicities for which dose modifications are listed above.

Grade	Action and Dose Modification
Grade 1 or transient Grade 2	No intervention

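### The grade 2 pneumonitis stop row, taken literally, acts at the third episode, which does not fit the 45 mg floor reached after the first

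*Protocol*

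**What the plan says.** Section 3.5 of the Protocol sets three dose levels in Table 1: 60 mg at the start, then 45 mg, then 30 mg. Non-infectious pneumonitis has its own table.

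- Grade 1: no change.
- Grade 2: interrupt until recovery to grade 1 or better, then re-treat one dose level lower. Footnote a qualifies this: "Not applicable for 45 mg dose level. No re-escalation is allowed after the dose reduction".
- "Grade 2 second re-occurrence": permanent discontinuation.
- Grades 3 and 4: permanent discontinuation.

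The text under the table adds a floor, "The lowest dose level for patients with non-infectious pneumonitis is 45 mg", and a consequence: "if a patient is already on the 45 mg dose level and cannot tolerate treatment study treatment will be discontinued permanently".

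Three other provisions of section 3.5 bear on the point. The general non-hematologic table opens with "This section does not refer to those non-hematologic toxicities for which dose modifications are listed above". The text with Table 1 says of a patient at 30 mg that "if there is an indication for further dose reduction, the patient must permanently discontinue copanlisib". It also limits holds: "Patients requiring treatment to be held for >4 weeks will be taken off treatment".

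**The concern.** A re-occurrence is an event after the first occurrence, so a second re-occurrence is the third episode. A rule that stops at the third episode needs an instruction for what to give after the second, and the table has none. It allows one reduction for pneumonitis, from 60 to 45 mg, which provides for one re-treatment.

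At stake is consistent handling of a lung toxicity. At a second grade 2 episode, one site could stop because nothing permits re-treatment, while another could resume at 45 mg because the stop row has not literally been met. The rest of the protocol is cautious here: grade 3 stops treatment at once, and section 2.1.17 bars patients with past or current interstitial pneumonitis. A label that implies another exposure after two on-drug episodes sits badly with that caution.

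**Working it through.** The protocol gives no figure to reproduce. The first check traces the dose path and the second bounds how many patients could be affected.

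**Dose path from 60 mg, following the table literally**

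| Grade 2 episode | Dose at onset | Row that applies | Re-treatment dose given |
|---|---|---|---|
| 1 (first occurrence) | 60 mg | Grade 2 | 45 mg, no re-escalation |
| 2 (first re-occurrence) | 45 mg | Grade 2; the stop row is not yet met | None: footnote a removes the step down |
| 3 (second re-occurrence) | Reached only by resuming at 45 mg | Stop row | Permanent discontinuation |

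If the row meant the second occurrence, episode 1 would lead to 45 mg and episode 2 to a permanent stop. That agrees with footnote a and with the floor.

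**Whether other text fills the gap at episode 2**

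- The floor sentence orders a stop at 45 mg but ties it to not tolerating treatment, which is undefined. A site could argue that a grade 2 event that recovered was tolerated.
- The general non-hematologic table excludes toxicities that have their own rules, so its stepwise resumption does not apply to pneumonitis.
- The Table 1 rule on a further indicated reduction is written for 30 mg. It settles pneumonitis in a patient already at 30 mg for another reason, but not the 45 mg case.

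**Number of patients**

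Inputs from the Protocol: the accrual goal of 35 (Schema), and study 12871 in section 1.3, where "no pneumonitis was reported in the 48 patients with solid tumors treated in this study".

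- One-sided 95% exact upper bound for 0 of 48: 1 − 0.05^(1/48) = 0.0605. Times 35 gives 2.12 patients, any grade.
- Two-sided 95% version: 1 − 0.025^(1/48) = 0.0740. Times 35 gives 2.6 patients.

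Only a recurrent grade 2 case, or a grade 2 case in a patient already at 45 mg, reaches the disputed step. The Protocol gives neither the grade 2 share nor the recurrence rate, so both are assumed here. Ceiling for the recurrent path = 2.12 × grade 2 share × recurrence:

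- Low: 2.12 × 0.25 × 0.10 = 0.05
- Middle: 2.12 × 0.50 × 0.25 = 0.26
- High: 2.12 × 0.75 × 0.50 = 0.79

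These start from an upper confidence bound, so they are ceilings and not expected counts. They also take the study 12871 rate to carry over to this trial.

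**The case against.** The strongest answer is that the page already resolves the case. Footnote a withdraws the only re-treatment dose at 45 mg, the next sentence makes 45 mg the floor and orders a stop for patients who cannot tolerate it, and the Table 1 text uses the same logic at 30 mg. No line permits resumption at 45 mg, so the unsafe reading requires a site to supply a dose that the table withholds. On this view the row is a slip for second occurrence. The evidence of harm is also thin: the three pneumonitis cases described in section 1.3 were all grade 3 in follicular lymphoma, which this table would have stopped at once, and section 2.1.12 excludes indolent lymphoma.

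Most of this stands. A reader might infer that the protocol authorises re-challenge after a second grade 2 episode. It does not; it is only silent on the dose, and the nearby text leans the other way. Nor is it a strict contradiction, because footnote a could be read as keeping the dose at 45 mg, although the protocol never says so. A reader might also take the section 3.4 adverse event list, which puts pneumonitis in the column for up to 20%, as implying 0.20 × 35 = 7 patients. That list's group term includes dyspnea, so it is not a rate of non-infectious pneumonitis.

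The objection does not remove the row itself. It is an operative stopping rule, and followed as worded it does not stop a patient at the second episode.

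**Conclusion.** The point holds as a minor inconsistency in a safety stopping rule. The row's literal stop at the third grade 2 episode does not fit a 45 mg floor that a patient starting at 60 mg reaches after the first. The adjacent text already favours stopping at the second episode, so the row is what needs correcting.

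Few if any of the 35 patients would be affected. The any-grade upper bound is about 2.1 patients and the ceiling for the recurrent path is about 0.05 to 0.8, the latter resting on assumed grade 2 shares of 25% to 75% and recurrence of 10% to 50%. Even that ceiling counts patients who reach the disputed step; it does not count patients who are re-exposed. No endpoint, sample size or statistical result depends on this, and nothing here supports a claim that it does.

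**What to change.** Two edits in an addendum:

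1. Change the stop row to: *Grade 2, second occurrence (first recurrence): permanent discontinuation.*
2. Have footnote a state that grade 2 non-infectious pneumonitis at 45 mg means permanent discontinuation.

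Keep the sentence on patients who cannot tolerate 45 mg. Replacing its condition with a pneumonitis-specific one would narrow a broad stop: a patient with prior pneumonitis held at 45 mg who then had, for example, recurrent grade 3 diarrhea would meet the floor with no stated action, while the general table would send that patient to 30 mg. If the sentence is touched at all, add *including any grade 2 or higher non-infectious pneumonitis*.

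The cost is one row and one footnote. The downside is that a very few patients stop one episode earlier. Any patient already at 45 mg for another toxicity would stop at the first grade 2 episode.

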3.6 Supportive Care

All supportive measures consistent with optimal patient care will be given throughout the study. Diarrhea, nausea and vomiting have all been reported with copanlisib. Supportive measures with anti-diarrheals and anti-emetics are recommended per investigator discretion or local institutional guidelines for emergence of treatment related symptoms.

3.7 Duration of Agent-specific treatment

In the absence of treatment delays due to adverse event(s), treatment may continue until one of the following criteria applies:

- Extraordinary Medical Circumstances: If at any time the constraints of this protocol are detrimental to the patient's health, protocol treatment should be discontinued. In this event submit forms according to the instructions in the MATCH Forms Packet.
- Patient withdraws consent.
- Patient experiences unacceptable toxicity.
- Non-protocol therapies are administered.
- Disease progression

3.8 Duration of Follow-Up

Refer to the MATCH Master Protocol for specifics on the duration of follow-up.

Rev. Add16 4. Study Parameters

4.1 Therapeutic Parameters for Copanlisib Treatment

NOTE: In addition to the study parameters listed in the MATCH Master Protocol, the below parameters must also be performed for patients receiving Copanlisib treatment.

NOTE: All assessments required prior to registration to treatment should be done \leq 4 weeks prior to registration to Steps 1, 3, 5, 7, excluding the radiologic evaluation and electrocardiogram (ECG).

Test/Assessment	Prior to Registration to Treatment	Treatment		End of Treatment	Follow Up ^F
		Every Cycle, prior to treatment	Every 2 Cycles		
H&P, Weight, Vital signs ^A	X	X ^I			X
Performance status	X	X ^I			X
CBC w/diff, including pits ^B	X	X ^I			X
Serum chemistry ^B	X	X ^I			X
Glucose monitoring ^K		X			
Hemoglobin A1c ^L	X				
Radiologic evaluation ^D	X		X ^D		X ^F
β -HCG ^C	X				
Toxicity Assessment ^G		X		X	X ^F
ECG ^J	X	X ^H		X	X
Tumor biopsy and blood sample for MATCH Master Protocol ^E					

A. History and physical, including vital signs and weight at the start of each cycle (up to 3 days before start of new cycle). Blood pressure will be measured prior to each copanlisib dose (no more than 4 measurements) until there are two consecutive results $< 150/90$ mmHg. On copanlisib infusion days, blood pressure will be measured at pre dose, 30 min after the start of infusion, right after the end of infusion, and 1 h and 2 h after the end of copanlisib infusion. Time window of ± 10 min is allowed for all post dose blood pressure measurements. Refer to Section 3.1.

B. Albumin, alkaline phosphatase, total bilirubin, bicarbonate, BUN, calcium, creatinine, fasting glucose, phosphorus, potassium, SGOT[AST], SGPT[ALT], sodium, magnesium and serum tumor markers (including LDH, PSA if appropriate). For eligibility purposes, participants with creatinine levels above institutional normal, Cockcroft-Gault will be used to calculate creatinine clearance. CBC w/diff, platelets and serum chemistries should be performed on cycle 1, day 1 (or up to 7 days prior), and at the start of each subsequent cycle (up to 3 days before start of new cycle). CBC with differential will be performed more frequently in patients with grade 4 neutropenia or thrombocytopenia until resolution to \leq grade 3. CBC and serum chemistries are only required in follow-up until values return to pre-treatment levels or until progressive disease. Please refer to the table in Section 3.1 regarding "Pre-dose glucose levels."

Rev. Add29 C. Blood pregnancy test (patients of childbearing potential) required prior to beginning treatment.

D. Disease measurements are repeated every 2 cycles for the first 26 cycles, and every 3 cycles thereafter until PD or start of another MATCH treatment step. The baseline evaluation should be performed as closely as possible to the beginning of treatment and never more than 6 weeks before registration to treatment step. For multiple myeloma patients, please refer to Section 6.4 of the MATCH Master Protocol for additional information on myeloma response criteria and the required disease assessments. Documentation (radiologic) must be provided for patients removed from study for progressive disease.

E. Additional blood specimens and/or biopsies are to be submitted from consenting patients per Section 9.3.2 of the MATCH Master Protocol.

E. Submit at the following time points, as applicable:

- For patients entering the study via the outside assay process (Appendix XIV of the MATCH Master Protocol), central IHC testing by the MD Anderson MATCH trial laboratory confirming expression of PTEN is required prior to receiving treatment assignment.
- Blood specimens are to be submitted at the end of Cycle 2 (prior to start of Cycle 3 treatment). If patient progresses or treatment is discontinued prior to Cycle 3, collect the blood at that time instead. On-treatment kits for blood sample collections will be automatically shipped to sites upon registration to the treatment step.
- Screening biopsies for additional aMOI assessments after registration to appropriate screening step, if applicable (Step 2 or Step 4).
- At end of all MATCH study treatments, blood specimens and/or research biopsy after consent and registration to Step 8.

Please refer to Section 4 of the MATCH Master Protocol to determine whether the patient proceeds to the next screening step or to follow-up (with a potential end of treatment biopsy for research purposes on Step 8). Samples are to be submitted as outlined in Section 9 of the MATCH Master Protocol. To order Step 2/4 Screening or Step 8 kits, complete the EAY131 Collection and Shipping Kit Order Form (See Appendix XII of the MATCH Master Protocol) and fax to [contact].

F. Every 3 months if patient is < 2 years from study entry, and every 6 months for year 3. Toxicity assessments and radiologic evaluations are not required to be done during Follow Up if progression has been previously reported; however if an adverse event occurs post treatment that meets the SAE reporting requirements, it still must be reported via CTEP-AERS, even if progression has occurred.

G. Site personnel should evaluate for toxicity and discuss treatment compliance with the patient in order to ensure the medication is taken correctly; this evaluation may be conducted by telephone or in person. The Toxicity Assessment is not required prior to Cycle 1, but is required every subsequent cycle.

H. As clinically indicated.

I. For Cycle 1, if the following tests/assessments occurred within 7 days of Day 1, they do not need to be repeated at this timepoint: H&P, Weight, Vital Signs; Performance Status; CBC w/diff, pits; Serum chemistry; Concomitant Medications.

J. Within 8 weeks of treatment assignment.

K. On Cycle 1 Day 1, glucose test (finger stick or serum glucose) is performed before starting copanlisib IV infusion at time 0 hour. On Cycle 1, Days 8 and 15 and all treatment days in subsequent cycles, glucose test is performed before starting copanlisib IV infusion at time 0 hour. Additional measurements to be performed at the clinic as clinically indicated at the investigator's discretion. Refer to Section [3.1](#).

L. Hemoglobin A1c (HbA1c) is to be tested at screening if patient has Type I or II diabetes mellitus. Refer to Section [2.1.9](#).

5. Drug Formulation and Procurement

This information has been prepared by the ECOG-ACRIN Pharmacy and Nursing Committees.

Availability

NO STARTER SUPPLIES MAY BE ORDERED. Subjects must be enrolled and assigned to the treatment subprotocol prior to submitting the clinical drug request to PMB.

Drug Ordering: NCI supplied agents may be requested by eligible participating Investigators (or their authorized designee) at each participating institution. Pharmaceutical Management Branch (PMB) policy requires that drug be shipped directly to the institution where the patient is to be treated. PMB does not permit the transfer of agents between institutions (unless prior approval from PMB is obtained – see general information) The CTEP-assigned protocol number must be used for ordering all CTEP-supplied investigational agents. The eligible participating investigators at each participating institution must be registered with CTEP, DCTD through an annual submission of FDA Form 1572 (Statement of Investigator), NCI Biosketch, Agent Shipment Form, and Financial Disclosure Form (FDF). If there are several participating investigators at one institution, CTEP-supplied investigational agents for the study should be ordered under the name of one lead investigator at that institution.

Submit agent requests through the PMB Online Agent Order Processing (OAOP) application (<https://ctepcore.nci.nih.gov/OAOP>). Access to OAOP requires the establishment of a CTEP Identity and Access Management (IAM) account (<https://ctepcore.nci.nih.gov/iam/>) and the maintenance of an “active” account status, a “current” password, and an active person registration status.

NCI Supplied Agent(s) – General Information

Questions about drug orders, transfers, returns, or accountability should be addressed to the PMB by calling [contact] Monday through Friday between 8:30 AM and 4:30 PM Eastern Time or email [contact] anytime.

Drug Returns: All undispensed drug supplies should be returned to the PMB. When it is necessary to return study drug (e.g., sealed bottles remaining when PMB sends a stock recovery letter), investigators should return the study drug to the PMB using the NCI Return Agent Form available on the NCI home page (<http://ctep.cancer.gov>).

Drug Accountability: The investigator, or a responsible party designated by the investigator, must maintain a careful record of the receipt, disposition, and return of agent received from the PMB using the NCI Investigational Agent Accountability Record Form for Oral Agents available on the NCI home page (<http://ctep.cancer.gov>). Maintain separate NCI Investigational Agent Accountability Records for each agent, strength, formulation and ordering investigator on this protocol.

Investigator Brochure Availability: The current versions of the IBs for PMB-supplied agents will be accessible to site investigators and research staff through the PMB Online Agent Order Processing (OAOP) application. Access to OAOP requires the establishment of a CTEP Identity and Access Management (IAM) account and the maintenance of an “active” account status, a “current” password, and active person registration status. Questions about IB access may be directed to the PMB IB coordinator at [contact].

